Upon presentation to the casualty unit at MRRH and/or within 30 minutes prior to each CT scan, the study team will approach the patient or the patient's surrogate/attendant for permission to scan the patient's cranium with the InfraScanner 2000TM (Image A) and following the CT scan with the second Infrascanner (Image B). If permission is granted, the study team member will sequentially measure the optical absorption for each of the 8 quadrants of the scalp (frontal, temporal, parietal, and occipital bilaterally). The device is engineered such that the light emitter and receiver are spaced 4 cm apart, allowing the light's intensity to be measured between adjacent light guides. This entire procedure, including greeting and scanning the patient twice should take <15 minutes. Should the patient obtain a subsequent CT scan(s) the number of scans the patient receives determines the number of potential data collections. The patient will be approached by the study team at the time of each CT scan and can decline participation during any individual encounter without withdrawing from the study.

The collection period for each research participant concludes within 30-days following his or her initial consent, patient or patient surrogate/attendant decision to withdraw from further participation, hospital discharge, or patient death; whichever occurs first.

[figure not shown]
6. Participant Recruitment and Compensation: Potential research participants will be approached by the research assistants. To avoid bias and potential coercion, the clinical team will not be involved in the participant recruitment. The research assistant will be graduate nurse. They will be trained in the consent process, and will make it abundantly clear that agreement or refusal to participate in the study will not influence the patient's care in any way.

Infrascanner Study PI: [name]

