7. Consent Process: After being made aware of the study by the research assistant and agreeing to hear more about the study, the prospective participant and/or the patient surrogate/attendant will be given more information about the study. Upon admission to MRRH for suspected head trauma, the research assistant will introduce the patient or the patient's patient surrogate/attendant to the presence of the study. If the consenting party agrees to hear about the study. The research assistant will greet the patient and will speak with patient and/or patient surrogate/attendant, thoroughly describing the protocol and reason for the study. All consenting study personnel will be trained in the consent process, and will provide ample reassurance to the patient or consenting party that the decision to participate will not, in any way, affect his/her medical care. Care will be taken to thoroughly answer all questions prior to obtaining final consent. The patient and/or patient surrogate/attendant will be clearly informed that the research protocol is completely optional, that participation will not affect the treatment they receive, and that, should they give consent, they are free to withdraw from the study at any time. They will be afforded indefinite time to make their decision to participate or withdraw from the study up unto: 1. 30 days following initial consent or 2. When they definitively will no longer receive brain CT scans / are discharged from medical care. The consent process will occur in the casualty unit at MRRH or at the CT scan of Mayanja Memorial hospital. The study team will be readily available to the patient, patient surrogate/attendant, and/or patient's relatives throughout the study for any questions or concerns they may have.

8. Data collection

Once the participant is identified he will be assessed whether they met the inclusion criteria of the study. In they do, they will then be consented and and enrolled in the study. Data Collection will follow the follow chat below.

Infrascanner Study PI: [name]

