Frontal Left/Right forehead, above the frontal sinus; Temporal In the Left/Right temporal fossa; Parietal Above the Left/Right ear, midway between the ear and the midline of the skull; Occipital Behind the Left/Right ear, midway between the ear and the occipital protuberance (Image B).

The difference in optical density (Δ OD) in each of the four symmetrical areas is calculated on a pair-wise basis from the following formula:

$$\Delta OD = \log_{10} \left(\frac{I_N}{I_H} \right) = \log_{10} \left(I_N \right) - \log_{10} \left(I_H \right)$$

where IN = the intensity of reflected light on the normal side, IH = the intensity of reflected light on the hematoma side.

In summary: The Infrascanner includes three components: (1) the Scanner, (2) the Disposable Shield and (3) a Cradle. The Scanner includes a safe NIR diode laser and a silicon detector. The light to and from the laser and detector is optically coupled to the patient's head through the disposable shield optical fibers. The optical fibers are long enough to reach through hair and contact the scalp. The optical fibers are placed 4 cm apart allowing optimal detection of hematomas. The extended fiber optics eliminates the need to shave off any hair. And because the fiber optic piece is disposable it prevents cross contamination. The detected light passes through an optical NIR band-pass filter in order to minimize background light interference. Electronic circuitry is included to control laser power and the detector signal amplifier gain. The detector signal is digitized and analyzed by a single board computer, SBC, in the Scanner. The SBC receives the data from the detector and automatically adjusts the settings of the Scanner to ensure good data quality. The data is further processed by the SBC and the results are displayed on the screen. Readout of the scan provides information on the severity of a hematoma and identifies the region of the brain bleeding. A higher optical density in the scanned region indicates a larger hematoma (20).

Infrascanner Study PI: [name]

- 12. Risk/Benefit Assessment: There are neither any specific clinical benefits to the research participant, nor are there any direct incentives, financial or otherwise, provided to the research participant. There is no known health risk of interval, short-term. All data obtained with the Infrascanner 2000TM will be blinded from physicians participating in the care of study patients to avoid any deviation from standard of care.

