- **13. Costs to the Subject:** No additional costs to the patient will be incurred as a result of this add-on research protocol. The participant will receive UGX 15000 as stipend for participating in the study.
- **14. Statistical Considerations:** Objectives: The primary objective of this study is to estimate the test characteristics (sensitivity, specificity, and the false positive and false negative rates) of the portable NIR-based device (InfraScanner 2000TM) in the identification of any size hematoma among patients hospitalized at MRRH who have sustained or who are suspected to have sustained head trauma. For those who go on to obtain CT scans, the results of the CT scan(s) will serve as the gold standard. The sensitivity, specificity, and the false positive and false negative rates will be estimated at the patient level and at the scan level. Approximately 10% of patients are anticipated to have more than one CT scan.

A secondary objective is to estimate the test characteristics of the InfraScanner 2000TM in identification of hematomas within its detection limits (volume >3.5 mL and depth <2.5 cm) compared to CT scan results as the gold standard.

Exploratory objectives include:

- 1. Examining the impact of factors such as hematoma type, location, and patient age on test characteristics of the InfraScanner 2000TM
- 2. Determining the minimum resolution detectable by the InfraScanner 2000TM
- 3. Analyzing the effects of extracranial hematomas, lacerations, and swelling on the performance characteristics of the device
- 4. Estimating Receiver Operating Characteristic (ROC) curves with patient and scan as the units of analysis (20).

Study Design:

a) Eligibility: All patiets with suspected TBI and meet the WHO and Brain Injury (BI) trust criteria for CT scaning

Inclusion criteria

Patients with suspected TBI above 12 years with suspected TBI and meet the BI criteria for CT scan

Patients that present with CT that was taken within 30 minutes

Patients with TBI that occurred more than 48 hours

Patietns with suspected TBI who present to Mayanja Memorial Hospital for CT scan but managed at Mbarara Regional Referral Hospital

Patients who do not present with CT scan images and cannot afford to pay for a CT Scan, will be included in the study and the study team will pay for their scans.

Exclusion Criteria

Infrascanner Study PI: [name]

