With 68 patients with positive findings of hematoma (i.e. CT-proven SDH/EDH) sensitivity can be estimated to within at most +/- 0.099 with 90% confidence. Assuming 20% of patients have true hematomas detected, 340 patients who obtain CT scans must be accrued (10). We estimate that 50% of patients will obtain CT scans. Accounting for this, and allowing for a 5% dropout rate the required sample size for this trial is 720 total participants. With 272 patients having negative findings for hematoma via CT, specificity can be estimated to within at most +/- 0.05 with 90% confidence.

d) Interim Analysis

Infrascanner Study PI: [name]

An interim analysis will be conducted once 150 patients with accompanying CT scans have been enrolled in the study to estimate the prevalence of hematomas at MRRH. The adjusted 90% confidence interval estimate for sensitivity will also be constructed. Based on these results the trial may be amended to enroll fewer or more patients.

e) Accrual

It is anticipated that at least 120 patients per month will be accrued and studied at MRRH. Study enrollment should thus be completed within approximately 6 months. The collection period for each research participants concludes within 30-days while in hospital following his or her initial consent, patient or surrogate/patient attendant decision to withdraw from further participation, or hospital discharge, or patient death; whichever occurs first.

15. Data and Safety Monitoring: Patients will be under continuous supervision during the entirety of each data collection period. Outside the ~10-minute window of each collection period, the patient is not subjected to any research intervention or influenced by the research in any way. As part of their treatment, patients will be under hospital care for their diagnoses for which they were admitted, and the research team will be in continual contact with the team regarding their clinical status and enrollment in the study.

The PI will be responsible for securing and monitoring the data, including a quarterly review of data storage procedures.

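### The study-paid CT and the stipend conflict with the protocol's own statements that taking part brings no benefit or incentive and leaves care unaffected

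*Combined protocol and SAP*

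**What the plan says.** All references are to the combined protocol and SAP.

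- **Section 14(a), inclusion criteria:** those lacking both CT images and the means to buy them "will be included in the study and the study team will pay for their scans". Payment is written as part of inclusion.
- **Section 13, Costs to the Subject:** "The participant will receive UGX 15000 as stipend for participating in the study".
- **Section 12, Risk/Benefit Assessment:** it opens with "There are neither any specific clinical benefits to the research participant" and then rules out inducements as well: "nor are there any direct incentives, financial or otherwise, provided to the research participant". The study-funded CT is not mentioned there.
- **Section 6, Participant Recruitment and Compensation:** research assistants are to make clear that "agreement or refusal to participate in the study will not influence the patient's care in any way".
- **Section 7, Consent Process:** the patient or surrogate is to be told "that participation will not affect the treatment they receive".
- **Section 15, Data and Safety Monitoring:** outside a collection window of about 10 minutes, "the patient is not subjected to any research intervention or influenced by the research in any way".

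Two pieces of context matter. Section 3 says that in less developed countries a CT often costs several months' income, and that CT sorts patients into surgical or medical management. Section 9 expects most participants to be neurologically or cognitively impaired, with consent coming from a surrogate or attendant.

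**The concern.** Sections 13 and 14(a) each provide something that the other sections say is not provided. The stipend is a payment for participating, and Section 12 rules out direct incentives, financial ones included. The funded CT is an examination that Section 3 describes as guiding management. It goes to people defined by their inability to buy it, while staff are directed to say that participation has no bearing on care or treatment.

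At stake is the accuracy of what patients and surrogates are to be told, and the completeness of the risk/benefit section on which a minimal-risk judgement rests. Section 6 itself names avoiding potential coercion as an aim of the recruitment procedure.

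There is a smaller statistical consequence. Paying for scans changes who receives the reference standard. Nothing in the visible text says that the source of payment is recorded, so the prevalence estimated at the interim analysis could not be described separately for study-paid and other CT patients.

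**Working it through.** **Step 1. Stipend against Section 12.** Section 13 attaches the payment to participation and does not limit it to a subgroup. Section 12 excludes direct incentives of any kind. Both cannot stand. No inference is needed, and the conflict covers every participant.

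**Step 2. Study-paid CT against the assurances.** Set each statement against two kinds of participant:

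| Statement | Section | Directed to be told to patients? | CT obtained without study payment | CT obtained only because the study pays |
|---|---|---|---|---|
| No direct incentive | 12 | Not stated | Contradicted by the stipend | Contradicted by the stipend |
| No specific clinical benefit | 12 | Not stated | No conflict | Does not fit |
| Joining or declining does not influence care | 6 | Yes | No conflict | Does not fit |
| Participation does not affect treatment | 7 | Yes | No conflict | Does not fit |
| No research influence outside about 10 minutes | 15 | Not stated | No conflict | Does not fit: the CT lies outside the window |

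The last column rests on an inference: without study payment, these patients would not get the CT. Section 14(a) defines them as unable to afford one, and no section offers the paid scan to a patient who declines. The inference is reasonable, but no section says what happens to such a patient.

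**Step 3. Can the affected group be sized?** The only relevant figures are in Section 14(c). They reproduce:

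- 68 CT-positive patients / 0.20 prevalence = 340 patients with CT.
- 340 / 0.50 CT uptake = 680.
- With 5% dropout, 680 / 0.95 = 716 (or 680 × 1.05 = 714), against 720 stated.

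The 50% uptake is given without saying whether study-paid scans are included. If they are, the affected patients lie inside the half with a CT. If they are not, they come from the other half, and true uptake would exceed 50%. No share unable to pay is given. Section 14(b) still expects some participants never to have a CT. The group therefore cannot be sized.

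**Step 4. What could a payer field support?** The worst-case 90% half-width for a proportion is 1.645 × √(0.25/n).

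- n = 68: 1.645 × √(0.25/68) = 0.0997, matching the plan's 0.099 apart from truncation.
- If half of the 68 positives were study-paid (assumed), n = 34: 1.645 × √(0.25/34) = 0.141.

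Sensitivity by payer would thus be estimated only to about ±0.14 in each group.

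For prevalence at the interim analysis (150 CT patients), using the planned 20%:

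- All 150: 1.645 × √(0.20 × 0.80/150) = 0.054.
- An assumed even split, 75 per group: 1.645 × √(0.20 × 0.80/75) = 0.076.

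That is usable as description, but not as a test of a difference.

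**The case against.** The strongest reply is that the study pays for an examination already indicated. The general eligibility line in Section 14(a) requires patients to meet published criteria for CT, Section 13 calls the work an add-on protocol, and Section 12 can be read as covering only the device scan, whose results are withheld from the treating team. On that reading the assurances mean that nobody is penalised for refusing. Part of this stands: whether the CT should be called a study procedure is debatable. But an indicated scan is not necessarily an obtained one, and the Section 6 assurance covers agreement as well as refusal. The reply also leaves the stipend conflict untouched.

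A reader might infer more than the documents support:

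- **That consent rests on false statements.** Section 5 refers to an approved verbal script that is not in the documents. It may disclose both the scan and the stipend. The sentences in Sections 12 and 15 are not said to be read to patients; only the assurances in Sections 6 and 7 are.
- **That the ethics committee was kept in the dark.** The paid CT and the stipend are both printed in the protocol. They are simply absent from the risk/benefit section.
- **That roughly half of the participants are affected.** Step 3 shows why the 50% figure cannot be used in this way.
- **That the case mix or the accuracy estimates are biased.** No section shows that willingness to join varies with ability to pay. Paying for scans could instead reduce selection, by giving a reference result to patients who would otherwise lack one.

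Nor can it be said that payer is definitely not recorded. Section 8 refers to a data-collection chart that is not visible in this copy.

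**Conclusion.** The point holds as an inconsistency in the stated consent and risk/benefit text, and it should be corrected. The stipend contradicts Section 12 for all participants, on the wording alone. For patients whose CT is obtained only because the study pays, the assurances directed in Sections 6 and 7, the no-benefit statement in Section 12 and the no-influence statement in Section 15 do not fit Section 14(a). This second part assumes that such patients would otherwise go without the scan. Their number is unknown.

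The finding concerns what the protocol directs staff to say, not what was said. It does not invalidate the planned accuracy estimates or the sample size, and it takes no position on who should receive a CT.

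**What to change.** - Reconcile Sections 6, 7, 12, 13, 14(a) and 15, and check the verbal script against the result.
- Disclose the study-paid CT and the stipend at consent, and qualify the care, treatment and no-incentive statements accordingly.
- Mention the study-funded CT in the risk/benefit section.
- Record for each CT who paid (routine care, the patient or the study), unless the data-collection chart already does so. Report hematoma prevalence by payer descriptively, including at the interim analysis. Any accuracy by payer should be descriptive only, for the reason in Step 4.

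Who should receive a CT remains a matter for the clinical team and the ethics committee.

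The cost is a protocol and script wording amendment and at most one data field. It adds no patients or procedures.

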Patients who present died Patients with images other than Mayanja Memorial Hospital and Mbarara Regional Referral Hospital

b) Standard of comparison:

All patients entered into the trial will undergo at least one cranial scanning using the InfraScanner 2000TM at the time of presentation. For patients who go on to get a CT scan, they will be scanned using the InfraScanner 2000TM within 30 minutes of each subsequent CT. Patients and care providers will be blinded to the results of InfraScanner 2000TM. The standard for comparison will be determined as follows. A CT result that is positive for hematoma will be considered a true positive and a CT result that is negative for hematoma will be considered a true negative. For patients who never go on to obtain a CT scan, their InfraScanner 2000TM results will be analyzed in the context of clinical data.

Definitions of Sensitivity, Specificity, False Positive, False Negative: Let A^+ denote the event that the test is positive for hematoma and B^+ denote the event that a hematoma is present. Sensitivity, $P(A^+/B^+)$, will be defined for each patient (scan) as the probability that a true hematoma as determined by CT scan will be detected (21). Similarly, let A^- denote the event that the test is negative for hematoma and B^- denote the event that a hematoma is not present. Specificity, $P(A^-/B^-)$, will be defined as the probability of being negative for hematoma on the InfraScanner 2000TM scan within 30 minutes of CT given the patient has no hematoma present.

The false positive rate will be defined as $P_{F^+} = P(B^-/A^+) = P(A^+/B^-)[1-P(B^+)]/P(A^+)$. Similarly, the false negative rate will be defined as $P_{F^-} = P(B^+/A^-) = [1-P(A^+/B^+)]P(B^+)/[1-P(A^+)]$. Estimates for the false positive and false negative rates will be provided for a range of values for the prevalence of hematomas.

c) Sample Size

Computation of the required number of patients is based on estimating the sensitivity of each method to within at most \pm 0.10 with 90% confidence. The 90% confidence interval for the sensitivity is given by $P_{Sens} \pm$ 1.645*SE(P_{Sens}) where SE(P_{Sens})= [(P_{Sens})(1- P_{Sens})/N; N denotes the number of true positives.

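### No masking of the device operator to CT is stated, yet device readings taken after CT can enter the primary accuracy estimates

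*Combined protocol and SAP*

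**What the plan says.** **Masking.** Two statements cover it, and both concern who may see the device result. Section 14(b) says "Patients and care providers will be blinded to the results of InfraScanner 2000TM". Section 12 says "All data obtained with the Infrascanner 2000TM will be blinded from physicians participating in the care of study patients", and the reason given there is to protect standard care, not the accuracy estimate.

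**Order of device scan and CT.** Section 5 plans a device scan at presentation and/or before each CT, and another "following the CT scan with the second Infrascanner (Image B". The inclusion criteria in Section 14(a) admit "Patients that present with CT that was taken within 30 minutes". Section 14(b) says of patients who get a CT that "they will be scanned using the InfraScanner 2000TM within 30 minutes of each subsequent CT". It does not say whether the analysed scan comes before or after the CT, or which reading counts when there are two.

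**Operator.** Under Section 5, "the study team member will sequentially measure the optical absorption for each of the 8 quadrants of the scalp". Section 11 says of the readout: "The data is further processed by the SBC and the results are displayed on the screen". Section 15 adds that "the research team will be in continual contact with the team regarding their clinical status and enrollment in the study".

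**The concern.** In an accuracy study the index test should be read without knowledge of the reference standard. Here the device result is withheld from those who might act on it, but the CT result is not expressly withheld from the person who produces the device result.

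The scanner computes its own reading, so bias would have to enter through the operator's handling: how the fibres are seated through hair at eight sites, whether a site is measured again, or which of two readings is carried forward. Knowing that a bleed is present, and on which side, could turn some misses into detections. Knowing that the CT is clear could turn some false alarms into negatives. Both errors favour the device.

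The results are intended to support a later trial of the device as a stand-alone tool where CT is unavailable (Section 3, Aim 2). An optimistic error is the costly direction for that purpose.

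**Working it through.** **1. Can a post-CT reading arise?** Yes, by three routes.
- The second device scan in Section 5 follows the CT by design.
- A patient who arrives with a CT already done can only have a first device scan after it.
- Section 14 expects about 10% of patients to have more than one CT, and Section 5 repeats device scanning at each. From the second CT on, even the pre-CT reading follows an earlier CT. This affects the scan-level analysis.

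**2. Can the operator learn the CT result?** The plan does not say so, but nothing prevents it. Eligibility depends on whether CT images exist, when they were taken and where. Consent may take place at the CT site (Section 7). The research and clinical teams are in continual contact (Section 15).

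**3. Can such a reading be analysed?** Yes. The timing rule in Section 14(b) is met on either side of the CT, and no reading is named as primary.

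**4. The plan's own precision.** The 90% half-width is 1.645 × √[p(1−p)/n].
- Sensitivity, p = 0.5, n = 68: 1.645 × √(0.25/68) = 0.0997 (stated as 0.099).
- Specificity, p = 0.5, n = 272: 1.645 × √(0.25/272) = 0.0499 (stated as 0.05).
- Sensitivity, p = 0.86 (the Duke any-size figure in Section 3), n = 68: 1.645 × √(0.86 × 0.14/68) = 0.069.

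The sample-size chain also reproduces: 68/0.20 = 340; 340/0.50 = 680; 680/0.95 ≈ 716, against 720 stated. Masking the operator changes none of these inputs.

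**5. Possible size of the bias.** Let s be true sensitivity. Let q be the share of CT-positive patients whose analysed reading was taken with knowledge of CT, and r the share of misses among them that become positive. Then apparent sensitivity = s + q × r × (1 − s). The documents give neither q nor r, so the values below are assumptions.

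| s | q | r | Apparent | Bias (points) | Half-width, n = 68 |
|---|---|---|---|---|---|
| 0.86 | 0.25 | 0.25 | 0.869 | +0.9 | 0.069 |
| 0.86 | 0.50 | 0.25 | 0.878 | +1.8 | 0.069 |
| 0.86 | 0.50 | 0.50 | 0.895 | +3.5 | 0.069 |
| 0.70 | 0.25 | 0.25 | 0.719 | +1.9 | 0.091 |
| 0.70 | 0.50 | 0.50 | 0.775 | +7.5 | 0.091 |

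The same formula applies to specificity. At the Duke figure of 0.96, q = r = 0.25 adds 0.04 × 0.0625 = 0.0025, and q = r = 0.5 adds 0.04 × 0.25 = 0.01.

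The sample size does not appear in the bias term, so enrolling more patients narrows the interval around a shifted estimate.

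**The case against.** Much of the case for leaving the plan alone is fair.

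- **The plan is silent; it does not say the operator is unmasked.** A reader might infer that operators will see the CT. The text does not say that, and the data-collection chart that Section 8 refers to is not readable in the available text. What stands is that no masking provision is stated.
- **The first pre-CT reading is clean.** Patients who arrive without a CT and are scanned beforehand are not exposed at their first CT. If that reading is the one analysed, they contribute no bias. This is why values of q near 1 do not fit the plan.
- **The device limits operator influence.** Positions are defined, all eight are measured, settings adjust automatically and the result is computed. No option to repeat a site is described, although none is ruled out. Misses below the detection limits (volume and depth, Section 14) may not be recoverable by better placement. The value of r is therefore unknown and could be small.
- **CT readers may already be masked.** They are covered if they count as care providers under Section 14(b). The text does not settle this.
- **Admitting patients who arrive with a CT might look like a contradiction of the pre-CT timing in Section 5.** It is not one: that sentence also allows an approach at presentation, which covers these patients.

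These points limit the size of the bias. They do not close the gap, because the timing rule still admits post-CT readings and the choice between two readings is left open.

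**Conclusion.** The point holds as an omission with a definite route to bias. As written, the plan lets device readings taken with knowledge of CT into the primary estimates, and the likely direction favours the device on both sensitivity and specificity.

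The size cannot be derived from the documents. At a true sensitivity of 0.86, it is +0.9 points with q = r = 0.25 and +3.5 points with q = r = 0.5. The larger figure is about a third of the stated half-width (0.035/0.099) and about half of the half-width at 0.86 (0.035/0.069). With smaller q or r it is negligible.

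A reader might conclude that the bias could use up the whole stated uncertainty. The documents do not support that. At 0.86 it would take every CT-positive patient analysed from a CT-informed reading, with half of all misses converted, to reach 0.07. That is still below the stated 0.099, and a plan with pre-CT scans does not imply it.

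The change should be made because it is cheap and because a larger sample would not correct this error.

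**What to change.** Add to Section 14(b):

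1. The operator records and locks each device result before seeing the CT image or report. For patients who arrive with a CT, the operator is not shown it. For every reading, the operator records whether they were unaware of the CT result.
2. The CT used as reference is read without knowledge of the device result.
3. The primary analysis uses the reading taken blind to CT, normally the pre-CT reading at the first CT. Post-CT and unblinded readings are reported separately, and the all-readings result is given as a sensitivity analysis.

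**Cost.** This takes protocol wording and one yes/no item on the case report form. Recruitment is already done by research assistants outside the clinical team (Section 6), so no extra staff should be needed.

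The real cost is precision. CT-positive patients with only an unblinded reading leave the primary table. If, for example, 34 of 68 remained, the half-width would be 1.645 × √(0.25/34) = 0.141 at p = 0.5, which misses the ±0.10 target, or 1.645 × √(0.86 × 0.14/34) = 0.098 at 0.86. The number excluded should therefore be reported. The planned interim look at 150 patients with CT is a convenient point to count blind readings and judge whether enrolment needs adjusting.
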